Appendix 1 Classification and Suggested Treatments for Acute Hypersensitivity Reactions

Severity of Symptoms	Treatment	Investigational product
Mild (Grade 1) Localised cutaneous reactions such as mild pruritus, flushing, rash, dizziness, headache, ≤ 20 point change in systolic blood pressure	 Evaluate subject, including close monitoring of vital signs At the discretion of the investigator, treat subject, for example with Antihistamine (eg, diphenhydramine HCL) oral or IV Paracetamol/acetaminophen 500-1000 mg Corticosteroids topical or systemic 	 Discontinue future administration of investigational product; OR, at the discretion of the investigator, continue investigational product administration and pretreating subject 1.5-0.5 hours prior to investigational product administration, for example with Antihistamine (eg, chlorpheniramine) 10 mg Paracetamol/acetaminophen 500- 1000 mg
Moderate (Grade 2) As above generalised rash or urticaria, palpitations; chest discomfort, shortness of breath, hypo- or hypertension with > 20 point change in systolic blood pressure. Drug fever $> 38^{\circ}$	 Treatment as for Mild (Grade 1) Normal saline (~500 ml) 	 Management as for Mild (Grade 1) If moderate event recurs in the same subject, discontinue future investigational product administration
Severe (Grade 3) or Symptomatic bronchospasm with or without urticaria, hypotension with ≥ 40 point change in systolic blood pressure, wheezing, angioedema, or stridor Life threatening (Grade 4) Defined as a reaction that is life threatening and requires pressor and/or ventilator support or shock associated with acidemia and impairing vital organ function due to	 Evaluate subject, including close monitoring of vital signs Maintain airway, oxygen if available Treat subject immediately, for example with Adrenaline/epinephrine 1:1000, 0.5-1.0 mL for bronchospasm, hypotension unresponsive to IV fluids, or angioedema. Dose and route as per local standard of care (e.g. SC for mild cases and IM for more severe cases) Secure IV access, normal saline (~500 to 1000 IV) IV corticosteroids (eg. such as hydrocortisone 100-200 mg or methylprednisolone 20-40 mg) If wheezing treat for asthma Antihistamine (eg. chlorpheniramine 10mg IV) 	 It is recommended to measure mast cell tryptase serum level within maximum 12 hours of the event or a serum sample to be collected and kept at -20C for the future analysis. Discontinue future investigational product administration

MedImmune CAM-3001	Protocol MI-CP219; Amendment 3 4 Apr2011; Final		
Severity of Symptoms	Treatment	Investigational product	
tissue hypoperfusion	 Paracetamol/acetaminophen 500-1000 mg Call emergency medical transport for transport to hospital if Grade 3 wheezing, hypotension or angioedema is unresponsive to single dose of adrenaline/epinephrine Grade 4 At the discretion of the investigator

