Pulmonary function testing at study sites will be performed to assess forced vital capacity (FVC), FEV_1 and DLCO. Both absolute values and the percentage of predicted normal value (Hankinson et al, 1999) will be recorded on the eCRF.

Pulmonary function tests including both spirometry and DLCO will be performed at Screening, Baseline (Day 1), on Days 29 and 85, and at the end of study (Day 169) and at the discontinuation visit for subjects withdrawing from the study prematurely.

Pulmonary function testing may be performed one day prior to dosing on Days 1, 29 and 85. In addition, if the screening pulmonary function tests are performed within 7 days of Day 1, then these tests do not need to be repeated at Day 1 if there is no clinically significant change in dyspnoea (Borg scale) or any clinically significant respiratory problem.

Any medically significant change from the screening pulmonary function tests, as interpreted by a pulmonologist, or in the event of a deterioration of more than 20% from baseline values, the event will be recorded as an AE. The subject will not receive any further treatment with CAM 3001 until the test has been repeated (within approximately 5 days) and the sponsor has confirmed that dosing can resume.

Modified Borg Scale (Dysphoea) and Oxygen Saturation

In addition, at each visit the investigator or qualified designee will assess the subject's dyspnoea as measured by the modified Borg scale score and measure oxygen saturation by pulse oximetry. The modified Borg scale (Borg, 1982) is a validated patient reported outcome that will be completed by subjects in the study. The safety assessor will evaluate completed questionnaires for subjects' perceived difficulty in breathing (dyspnoea). The scale ranges

MedImmune Protocol MI-CP219; Amendment 3 CAM-3001 Final from 0 (nothing at all) to 10 (maximal) with 10 being the maximal possible score. Higher scores indicate greater difficulty in breathing.

Oxygen saturation will be assessed by pulse oximetry at Screening, Baseline (Day 1) and at the time points specified in the Schedule of Subject Evaluations (Table 5.2-1) as part of respiratory system assessment.

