In the case that a subject develops any new significant respiratory symptoms/signs such as shortness of breath, difficulty in breathing, cough, experience an exacerbation of any current respiratory symptoms, or a significant deterioration in dyspnoea score as judged clinically significant by the investigator, the subject should not receive any further treatment with CAM-3001 and will be referred promptly to a specialist pulmonologist for further assessment. Upon resolution of symptoms/signs and exclusion of the diagnosis of any clinical significant respiratory event the treatment schedule could be resumed.

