6.4.1 Interruption or Permanent Discontinuation of Study Dosing in Individual Subjects

Interruption of dosing

MedImmune

The investigator may interrupt dosing if the subject experiences an event which, in the opinion of the investigator or the medical monitor, compromises subject safety such as active infection, deterioration of cardiopulmonary diseases meeting the exclusion criteria specified in Section 4.2.2 or the development of other complications. A subject with a neutrophil count below 1.5×10^9 /L will not receive any further investigational product until resolution of these symptoms. Similarly, a subject with a deterioration of pulmonary function (spirometry) or DLCO of more than 20% of the baseline values will not receive any further investigational product until the tests are repeated and an evaluation is performed by the pulmonologist that confirms the absence of any clinically significant lung problem. This opinion must then be communicated to the medical monitor. If the medical monitor gives approval to continue dosing, the scheduled dose should be administered at the latest within 5 days of the visit date. If dosing is not possible within 5 days, then the dose will be skipped at this visit. The next scheduled dose will be administered according to the protocol visit schedule.

Discontinuation of dosing

An individual subject will not receive any further investigational product if any of the following occur in the subject in question:

- 1) Withdrawal of consent.
- 2) Pregnancy.
- 3) Event which in the opinion of the investigator or the sponsor contraindicates further dosing such as illnesses or complications.
- 4) Any serious or life-threatening AE related to the investigational product.

MedImmune

CAM-3001

- 5) A change in concomitant RA therapy or other restricted medication during the treatment period of the study as described in Section 4.5.4.
- 6) A neutrophil count below 1.0×10^9 /L after administration of investigational product.

Subjects who are permanently discontinued from investigational product will be followed for the full study period (through Day 169). Where possible all study assessments should be completed, unless consent is withdrawn.

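### Appendix 1 and Section 5.3.1 give different dosing instructions for a first Grade 2 reaction with significant new shortness of breath, and 5.3.1 and 6.4.1 set different conditions for re-dosing after a lung-function fall of more than 20%

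*Protocol*

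**What the plan says.** **New respiratory symptoms.** Section 5.3.1 (text on the modified Borg scale and oxygen saturation) covers a subject who develops significant new respiratory symptoms or signs, and names shortness of breath. It says "the subject should not receive any further treatment with CAM-3001 and will be referred promptly to a specialist pulmonologist". Treatment may resume after the symptoms resolve and a clinically significant respiratory event has been excluded. It makes no exception for hypersensitivity reactions.

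**Acute hypersensitivity.** Appendix 1 describes the moderate (Grade 2) reaction as "As above generalised rash or urticaria, palpitations; chest discomfort, shortness of breath", with blood pressure changes and drug fever. Its investigational product column reads "Management as for Mild (Grade 1) If moderate event recurs in the same subject", and discontinuation is required on that recurrence. The Grade 1 instruction that it borrows offers two options: discontinue, or "at the discretion of the investigator, continue investigational product administration and pretreating subject". The column mentions neither a hold nor a pulmonologist.

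**Fall of more than 20% in lung function.** Section 5.3.1 (Pulmonary Function Testing) withholds CAM-3001 "until the test has been repeated (within approximately 5 days) and the sponsor has confirmed that dosing can resume". Section 6.4.1 withholds it until the tests are repeated and a pulmonologist's evaluation confirms that there is no clinically significant lung problem. That opinion goes to the medical monitor and, on approval, "the scheduled dose should be administered at the latest within 5 days of the visit date". Otherwise the dose is skipped.

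**The concern.** A site facing significant breathlessness soon after an injection can find two instructions in the same protocol. One leaves continued dosing to the investigator. The other withholds the drug and sends the subject to a pulmonologist. Sites that open different pages would treat like subjects differently.

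This matters more here than for most antibodies. Sections 1.3 and 1.5.1 present changes in lung macrophages as the predictable consequence of blocking GM-CSF, and Section 4.5.5 names pulmonary alveolar proteinosis as an event of special interest. Classification is also affected. The specific hypersensitivity event in 4.5.5 is limited to severe or life-threatening reactions, and the specific respiratory event needs confirmation by the study pulmonologist. A Grade 2 reaction with breathlessness handled under Appendix 1 alone may meet neither definition, whereas the same reaction handled under 5.3.1 would have been referred to a pulmonologist.

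For a lung-function fall, whether a pulmonologist's evaluation is needed before the next dose depends on which section the site reads.

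**Working it through.** No sample size, power or error rate is involved. The check is a comparison of the instructions, plus one small piece of timing arithmetic.

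**Step 1. One subject, two rules.** Take a first Grade 2 reaction that includes new shortness of breath judged significant.

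| | Section 5.3.1 | Appendix 1, Grade 2 |
|---|---|---|
| Trigger met? | Yes: significant new respiratory symptom | Yes: listed feature of the grade |
| Next dose | Withheld | Discontinue, or continue with pretreatment, at the investigator's discretion |
| Pulmonologist | Referral required | Not mentioned |
| Condition for resuming | Symptoms resolved and significant respiratory event excluded | None stated; discontinuation required only on recurrence |
| Refers to the other rule? | No | No |

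The conflict is confined to events that are both an acute hypersensitivity reaction and a significant respiratory symptom. Such events can occur: Section 6.3.3.4 defines acute hypersensitivity by features that include bronchospasm, hypoxia and pulmonary infiltrates.

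**Step 2. A fall of more than 20% in spirometry or DLCO.**

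| | Section 5.3.1 | Section 6.4.1 |
|---|---|---|
| Repeat test | Required, within about 5 days | Required, no time given |
| Pulmonologist's evaluation | Not listed for this trigger | Required |
| Approval | Sponsor | Medical monitor |
| Deadline for the held dose | None stated | 5 days from the visit date, otherwise skipped |

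The triggers differ too. Section 5.3.1 also withholds dosing for a medically significant change from screening as interpreted by a pulmonologist. The mandatory lung-function hold in 6.4.1 covers only the fall of more than 20%.

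**Step 3. Timing.** Let t be the day of the test relative to the visit (0, or −1 because 5.3.1 lets the test be done one day before dosing), and r the days until the repeat. Then days left for evaluation, approval and dosing = 5 − (t + r).

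- t = 0, r = 5: 5 − 5 = 0 days left.
- t = −1, r = 5: 5 − 4 = 1 day left.
- t = 0, r = 2: 5 − 2 = 3 days left.

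The repeat allowance can use up the re-dosing window, but only when it is taken in full or nearly so. The scheduled post-baseline tests that fall on dosing days are those at Days 29 and 85.

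**The case against.** The strongest reply is that the rules can be followed in sequence: hold, refer, and then resume with pretreatment once a respiratory event is excluded. Appendix 1 is headed as suggested treatments, offers discontinuation as its first option, and does not switch off 5.3.1. All of that is fair, and it narrows the point. What stands is that the protocol never states the sequence, and the appendix column read alone permits continued dosing where 5.3.1 withholds it.

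On the lung-function fall, 6.4.1 can be read as a fuller account of 5.3.1. The change of approver is largely nominal, because Sections 3.1 and 4.5.5 count the medical monitor within the sponsor's decision group. The pulmonologist's evaluation is not nominal: a site following 5.3.1 alone would not know that it is required.

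A reader might infer more than the text supports in three places.

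- *A three-way conflict that includes the general clause of 6.4.1* ("The investigator may interrupt dosing if the subject experiences an event which" compromises safety). This is a permission to interrupt. It does not authorise dosing that 5.3.1 withholds, and a site can obey both.
- *A dose that is bound to be skipped.* The 5 days for the repeat test is an outer limit, so an early repeat leaves time, and 6.4.1 says what happens if it does not.
- *A lung event that escapes the escalation review.* Section 6.3.3.4 makes acute hypersensitivity reactions and clinically significant worsening of dyspnoea reportable within 24 hours even when not serious. Section 4.5.5 puts all AEs and lung-function data before the reviewers. The event would be seen; how it is classified and whether the subject is re-dosed could vary.

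**Conclusion.** The concern holds in a narrow form. For a first Grade 2 acute hypersensitivity reaction with significant new shortness of breath, Appendix 1 and Section 5.3.1 give different dosing instructions and no order of precedence. For a fall of more than 20% in spirometry or DLCO, Sections 5.3.1 and 6.4.1 set different conditions for resuming, and the time allowed for the repeat test can consume the re-dosing window.

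The size cannot be put as a number. The protocol gives no expected frequency for either event, and the total of planned injections would only be a denominator. The consequence is inconsistent re-dosing and classification between sites, not concealment of events. The conclusion assumes that a site judges the breathlessness significant and also attributes it to a reaction to the injection; outside that overlap the first conflict does not arise. No view is taken on which clinical rule is right.

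**What to change.** 1. Reconcile the investigational product column of Appendix 1 (Grades 1 and 2) with the respiratory-symptom rule in Section 5.3.1. Add a cross-reference in both places stating which governs when a reaction includes significant new respiratory symptoms.
2. Reconcile Sections 5.3.1 and 6.4.1 so that a fall of more than 20% in spirometry or DLCO has one set of resumption conditions, stating whether the pulmonologist's evaluation is required and using one name for the approver. State also whether the wider trigger in 5.3.1 applies in 6.4.1.
3. Align the time allowed for the repeat test with the window for giving the held dose.

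The sponsor's clinicians choose the rules. The cost is protocol wording in three places. No new procedure is implied, because pulmonologist review already appears in both 5.3.1 and 6.4.1.

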6.1.2 Serious Adverse Events

A SAE is any AE that:

- Results in death
- Is immediately life-threatening

This term refers to an event in which the subject was at risk of death at the time of the event; it does not refer to an event that may have led to death.

• Requires inpatient hospitalisation or prolongation of existing hospitalization

In general, hospitalization signifies that the subject has been detained (usually involving at least an overnight stay) at the hospital or emergency ward for observation and/or treatment that would not have been appropriate in an outpatient setting.

• Results in persistent or significant disability/incapacity

The term disability means a substantial disruption of a person's ability to conduct normal life functions.

- Is a congenital anomaly/birth defect in offspring of the subject
- Is an important medical event that may jeopardize the subject or may require medical intervention to prevent one of the outcomes listed above.

Medical or scientific judgment should be exercised in deciding whether expedited reporting is appropriate in this situation. Examples of medically important events are intensive treatment in an emergency room or at home for allergic bronchospasm, blood dyscrasias, or convulsions that do not result in hospitalizations; or development of drug dependency or drug abuse.

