6.2 Assessment and Recording of Safety Parameters

6.2.1 Assessment of Severity

Assessment of severity is one of the responsibilities of the investigator in the evaluation of AEs and SAEs. The determination of severity should be made by the investigator based upon medical judgment and the severity categories of Grade 1 to 5 as generally defined below.

Grade 1	An event that is usually transient and may require only minimal treatment or therapeutic intervention. The event does not generally interfere with usual activities of daily living.
Grade 2	An event that is usually alleviated with additional specific therapeutic intervention. The event interferes with usual activities of daily living, causing discomfort but poses no significant or permanent risk of harm to the subject.
Grade 3	An event that requires intensive therapeutic intervention. The event interrupts usual activities of daily living, or significantly affects the clinical status of the subject. The event poses a

MedImmune CAM-3001	Protocol MI-CP219; Amendment 3 Final significant risk of harm to the subject, and hospitalisation may be required.
Grade 4	An event, and/or its immediate sequelae, that is associated with an imminent risk of death or is with physical or mental disabilities that affect or limit the ability of the subject to perform activities of daily living (eating, ambulation, toileting, etc).
Grade 5	The termination of life as a result of an event.

It is important to distinguish between serious criteria and severity of an AE. Severity is a measure of intensity whereas seriousness is defined by the criteria in Section 6.1.2. A Grade 3 AE need not necessarily be considered an SAE. For example, a Grade 3 headache that persists for several hours may not meet the regulatory definition of an SAE and would be considered a nonserious event, whereas a Grade 2 seizure resulting in a hospital admission would be considered an SAE.

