- 3) AEs that are considered to be allergic reactions related to investigational product
- 4) AEs that are considered to be anaphylactic or acute hypersensitivity reactions

For purposes of this protocol, acute hypersensitivity reactions are defined as AEs related to the injection of the investigational product itself that usually occur within the first 24 hours after injection, especially within minutes to a few hours. Acute hypersensitivity reactions can be characterised by a complex of signs and symptoms that include flu-like illness, fever, chills/rigors, nausea, urticaria, headache, bronchospasm, angioedema, hypotension, hypoxia, pulmonary infiltrates, acute respiratory distress syndrome, myocardial infarction, ventricular fibrillation and cardiogenic shock. For purposes of this protocol, a classification of acute hypersensitivity reactions is given in Appendix 1, with suggested treatment options. Final treatment is at the discretion of the investigator and should reflect local standard of care.

- 5) A deterioration of pulmonary function test by spirometry or DLCO more that 20% of the baseline values
- 6) Any clinically significant deterioration in dyspnoea score, as assessed by the investigator.

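### Section 6.4.1 and Appendix 1 give different re-dosing decisions for a first Grade 1 or 2 hypersensitivity reaction that is also serious

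*Protocol*

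**What the plan says.** Section 6.4.1 (Discontinuation of dosing) is worded as a mandatory rule: "An individual subject will not receive any further investigational product if any of the following occur in the subject in question". Item 4 of its list is "Any serious or life-threatening AE related to the investigational product". The item names no severity grade and makes no exception for hypersensitivity reactions.

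Section 6.1.2 lists the criteria for a serious event, any one of which is enough. One of them is "Requires inpatient hospitalisation or prolongation of existing hospitalization". Section 6.2.1 keeps grade and seriousness apart: "Severity is a measure of intensity whereas seriousness is defined by the criteria in Section 6.1.2". Its own illustration is that "a Grade 2 seizure resulting in a hospital admission would be considered an SAE".

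Section 6.3.3.4 settles the question of relationship for these reactions: "acute hypersensitivity reactions are defined as AEs related to the injection of the investigational product itself". It then points to Appendix 1 for their classification.

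Appendix 1 has a separate column for investigational product. For Grade 1, that column offers two options: stop, or continue with pretreatment if the investigator so judges. Grade 2 takes over the Grade 1 rule and adds one compulsory stop: "If moderate event recurs in the same subject, discontinue future investigational product administration". Grades 3 and 4 require a stop. The column does not mention seriousness.

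**The concern.** The two passages use different keys for the same decision. Section 6.4.1 uses seriousness plus relationship to product, and Appendix 1 uses symptom grade. Because the protocol itself says that the keys can diverge, some events satisfy the stopping rule in one place and still qualify for discretionary continuation in the other.

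What is at stake is re-exposure after a serious reaction, in what Section 1.5 describes as the first study of the subcutaneous route, with safety and tolerability among the primary objectives (Section 2.1). Staff handling a reaction are directed to Appendix 1 (Sections 4.5.3 and 6.3.3.4), and nothing in that table sends them to Section 6.4.1. A site could follow the table in good faith and depart from the stopping rule.

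**Working it through.** No sample size, error rate or event count enters this point, so the check is a comparison of texts.

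**Test case:** a first acute hypersensitivity reaction with Appendix 1 Grade 2 signs (for example generalised urticaria with chest discomfort), after which the subject is admitted to hospital.

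1. *Is it serious?* Yes. Inpatient hospitalisation alone meets Section 6.1.2. Section 6.2.1 confirms that Grade 2 does not prevent this, by the example it gives.
2. *Is it related?* Yes. Section 6.3.3.4 defines acute hypersensitivity reactions as related to the injection. The general rule in Section 6.2.2 points the same way, since an event counts as related unless a not-related test is met.
3. *Outcome under Section 6.4.1 item 4:* no further product.
4. *Outcome under Appendix 1, Grade 2:* stop, or continue with pretreatment on the investigator's judgement. The compulsory stop needs a recurrence, and this is the first event.

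| First reaction | Section 6.4.1 item 4 | Appendix 1, product column | Same decision? |
|---|---|---|---|
| Grade 1 or 2, not serious | Not triggered | Stop or continue, by discretion | No conflict |
| Grade 1 or 2, serious | No further product | Stop or continue, by discretion | **No** |
| Grade 3 or 4, serious | No further product | Stop | Yes |
| Grade 3, not serious | Not triggered | Stop | No conflict: 6.4.1 does not forbid the stop |

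Only the second row conflicts.

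5. *Does another passage settle it?* None was found. Section 6.4.1 does not cite Appendix 1, Appendix 1 does not cite Section 6.4.1, and neither is said to prevail. Section 6.3.3.4 leaves the final treatment to the investigator, but this concerns treatment of the reaction and not the decision to give another dose.
6. *Could serious in item 4 have been meant as severe?* That would bring the two texts into line, but Sections 6.1.2 and 6.2.1 define the words differently and warn against mixing them.
7. *Is hospital care after a reaction foreseen?* Yes. Section 6.4.3 allows for transfer to an emergency or hospital facility when the reaction warrants it. Transfer alone is not admission, but the test case is within what the protocol contemplates.

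**The case against.** The strongest reply is that both texts can be obeyed. Section 6.4.1 is mandatory and Appendix 1 only permits. Stopping is one of the options that Appendix 1 offers for Grades 1 and 2, and its title speaks of suggested treatments. On an ordinary reading, discretion is left only for subjects whom no mandatory rule has already stopped. It stands that a site that stops complies with both. It does not remove the point, because the protocol nowhere says that the discretion is limited in this way, and a site that uses it after a serious reaction breaches Section 6.4.1.

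Safeguards also reduce the risk. Acute hypersensitivity reactions and SAEs must be reported within 24 hours (Sections 6.3.3.4 and 6.3.2.1), the medical monitor reviews them (Section 6.4), doses are two weeks apart, and item 3 of Section 6.4.1 lets the investigator or sponsor stop the subject. New significant respiratory symptoms separately suspend dosing pending a pulmonologist's assessment (Section 5.3.1). Appendix 1 calls for emergency transport only in its Grade 3 and 4 row, so admission after a Grade 1 or 2 reaction should be uncommon. All of this stands. It makes an actual wrong re-dosing less likely, but it does not say which passage governs.

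A reader might also infer a second contradiction in the other direction, since a non-serious Grade 3 reaction must stop under Appendix 1 but is not named in Section 6.4.1. The documents do not support that. Section 6.4.1 does not forbid an additional stop, and its item 3 can cover the event.

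**Conclusion.** The point holds as an internal inconsistency, confined to one case: a first Appendix 1 Grade 1 or 2 acute hypersensitivity reaction that also meets a Section 6.1.2 seriousness criterion. It rests on reading serious and related as the protocol defines them, and on the absence of any stated precedence.

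Its size cannot be estimated from the documents and is likely small. A reader might be tempted to scale up the one Grade 2 urticaria among the 27 subjects given CAM-3001 in the first-in-human study (Section 1.4). That would not measure this conflict. The event occurred during a single-dose intravenous infusion in the 10 mg/kg cohort, whereas this trial gives 10 to 100 mg subcutaneously, and Section 4.5.3 says that such reactions are reported much less often by that route. The urticaria is also not among the events that Section 1.4 describes as serious, so it would not itself have met the conflicting case. The documents give no basis for the share of Grade 1 or 2 reactions that would be serious.

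Nor do the documents show that sites will in fact treat the same patient differently, or that exposure or discontinuation counts will shift between dose cohorts. They show only that the text permits two decisions where it should give one. Because the decision concerns re-exposure after a serious reaction, it is worth correcting despite its rarity.

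**What to change.** The sponsor should reconcile Section 6.4.1 and Appendix 1 so that a first Grade 1 or 2 reaction meeting a Section 6.1.2 criterion leads to one re-dosing decision, and should state that decision in both places. The product column of Appendix 1 should refer to the discontinuation list in Section 6.4.1, and that list should refer back to Appendix 1. Which clinical rule applies is for the sponsor to decide and is not judged here.

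The cost is about one line in each place, with no new procedure, visit or data item. Because the text governs dosing, the change would go through the approvals described in Sections 10.1 and 10.2, and it can be carried in the next amendment.
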